Phase 2: Pilot Randomized Controlled Trial: We will randomize 60 MA men into a 6-month pilot trial of the resulting text-enhanced PA intervention for MA men vs. a health education control. The procedures for recruitment, pre-trial screening, and monitoring derive from our team's experiences conducting similar trials (e.g., R21NR009864, R01NR011295, R01HL64342). See Figure 1. Although it is preferred that participants attend all visits in person, they will be informed during the telephone screening process that modified versions of study visit can be offered via phone in the event that they are not able to travel to the study site.

Figure 1: Phase 2 Randomized Controlled Trial Intervention Schema

Telephone Screening: To reduce the likelihood of adverse events, participants will be phone screened for factors that may increase risk of injury. Potential participants with medical or psychological problems that could make adherence with the study protocol difficult or dangerous will not be included. Exclusions include history of coronary heart disease, history of myocardial infarction, symptoms of angina, type 1 diabetes, uncontrolled hypertension, stroke, osteoarthritis, osteoporosis, orthopedic problems that would limit activity during the following six months, currently engaging in more than 90 minutes of activity per week or any other serious medical condition that would make physical activity unsafe. Other exclusion criteria will include hospitalization due to a psychiatric disorder in the past 3 years, BMI above 45 kg/m² and/or taking medication that may impair physical activity tolerance or performance (e.g., beta blockers). After screening is completed, eligible and interested participants must agree to be randomly assigned to one of the intervention conditions and provide written consent to participate in the research protocol. In addition, participants will be informed that in the event that they cannot attend an in-person visit at any of our study sites, they will have the option to complete the visit via phone. All in-person visits (including those occurring at our off-site UCSD facilities) will be conducted by our trained study staff. Descriptions of both in-person visits and phone visits are provided below.

In-Person Visits:

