Orientation/Measurement Visit: Following telephone screening for eligibility, interested individuals will be asked to attend an in-person orientation session in which a bilingual/bicultural research staff member will provide information about the study. During this session, all questions regarding participation in the study will be answered. Participants will then be asked to read and sign a consent form approved by the university's institutional review board. Participants will also complete anthropometric measures and an initial battery of psychosocial measures during this visit. Self-reported height and weight will be accepted. At the end of this visit, the participant will be given and instructed on how to use an accelerometer during the next seven days.

Baseline/Randomization Visit: One week after the orientations/measurement visit, the participant will return the accelerometer, complete a 10-minute treadmill walk at moderate intensity (3-4 miles per hour) to demonstrate understanding of moderate intensity activity, and complete the 7-Day Physical Activity Recall (PAR). At that time, participants will be randomly assigned to one of two conditions: 1) a text-message enhanced, Spanish language, individually tailored, print-based physical activity intervention; or 2) a Spanish language print-based health education control.

Months 1-6: After randomization, participants will fill out monthly mailed questionnaires for 6 months. Individuals randomized to the physical activity arm will receive individually tailored reports generated by a computer expert system along with messages appropriate for their stage of motivational readiness for physical activity adoption immediately following completion of the questionnaires. Those randomized to the health education control condition will also receive monthly mailed questionnaires and materials on health

topics related to cardiovascular disease, such as nutrition, physical activity, and stress management information. Participants will also be receiving text messages related to exercise or health and wellness depending on their group assignment. The schedule and amount of contact will be the same across conditions.

6 Month Assessment: All participants will be asked to attend an in-person visit at 6 months to recomplete all measures completed during the initial measurement visit and baseline visit.

Telephone Visit:

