meeting PA goals). At baseline participants will receive a pedometer, set a detailed PA goal, problem-solve around barriers to achieving their PA goal, and receive recommendations for walking/jogging routes, parks with athletic equipment and playgrounds, and other places to be active surrounding their work or home. They will receive regular mailings: weekly in month 1, bi-weekly in months 2 and 3, and monthly in months 4 to 6. Mailings consist of: 1) Manual matched to the participant's current level of motivational readiness to change, based on TTM; 2) Individually tailored computerized expert system feedback reports based on the participant's answers to monthly questionnaires (see Measures) that compares participants to their prior responses (progress feedback) and to individuals who are physically active (normative feedback) on: self-efficacy for PA and cognitive and behavioral strategies associated with PA behavior change (processes of change); 3) PA tip sheets addressing PA barriers. These print materials have been modified for MA men based on cultural themes identified during our formative work and trial (e.g. focus on family, team sports, "Machismo," etc.). Participants will also receive the text message intervention that will be developed as part of Phase 1 of this proposal. Based on our previous formative research, reviews of the literature, and theories of behavior change we anticipate using interactive, tailored, and culturally adapted text messages to: 1) increase accountability, 2) help navigate their environment, 3) increase competition, 4) increase motivation, 5) inform about local events, 6) focus on the family, 7) provide social support, and 8) increase the study's connectivity with participants. See Table 3 for proposed text messages, examples of text messages, and how they fit with SCT. Participants will receive \$5 per month to defray the costs of the text messages.

Table 3: Types of text messages to be used based on Qualitative Research and Social Cognitive Theory		
Social Cognitive Theory Construct	Intervention needs/Type of SMS	Types of text messages
Behavioral Capability/ Reinforcement	Need for Accountability/ Interactive, sent at specified times/days	1) Matched to day/time of exercise goal: "Have you exercised yet today? YES/NO"; "YES"; "Great job!" 2) Text message to log/collect info

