Reciprocal determinism	Built environment/ Tailored information	1) Places to be active near their home/work: "There's a great park with a soccer field at 1234 Main St."
Observational Learning	Increase Competition/ Group messages	1) Highlight success and encourage competition: "Someone reported over 12,000 steps yesterday, can you beat him?"
Outcome expectations/ Self-efficacy	Increase motivation through culturally relevant benefits and barriers/ Informational	1) Benefits of PA: "Having a rough day? Exercising is a great way to lower stress!" 2) Address barriers: "Work day seem too busy to be active? Look for places that you could get 10 min in, like during a lunch break"
Reciprocal determinism	Local activities/ Group messages	1) Text messages about community events: "Fiesta del Sol is this weekend, it's a great place to go walking with the family."
Observational Learning/ Self-efficacy	Focus on family/ Activity prompts	1) Text messages targeting the family: "Is the family home? Go on a walk together before dinner time!"
Observational Learning/ Outcome expectations	Social Support/ Participant Interactive	1) Way for participants to communicate with each other through group text messages via the server.

Health Education Control arm: The health education control arm will receive the publicly available NHBLI Spanish-language booklets on heart-healthy behaviors for Latinos, which include information on PA, diet, and stress management. Similar to intervention participants, control participants will receive tip sheets on related health topics. The health education content was vetted in our individual interviews with MA men who expressed a strong interest in receiving and reading these materials. Mailed contacts for the control group will be on the same schedule as the mailed contacts for the intervention condition (weekly month 1, bi-weekly months 2 and 3, and monthly months 4 to 6). Participants in the health education control arm will also complete monthly questionnaires relevant to the topics of their materials.

List of Measures

7-Day PAR Interview provides an estimate of total weekly minutes of PA.

Demographics measure will assess age, education, income, race, and marital status, and acculturation scale.

Stages of Change for Physical Activity (SCPA) measure has successfully been used to stage-match treatment.

Processes of Change for Physical Activity (POC) measure contains 10 subscales that address a variety of

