11. RECRUITMENT AND PROCEDURES PREPARATORY TO RESEARCH

Recruitment will follow a community-based, participatory model in that key community-based organizations and their leadership will be consulted and involved in recruitment. As in previous studies, we will employ multiple recruitment strategies. These strategies include:

- 1) We will recruit through local physicians (through the UCSD Department of Family Medicine) whose patient populations are largely Mexican and Mexican-American. Some of these physicians are Latino and bilingual. These physicians will provide potentially eligible participants (or their family members) with information on the study.
- 2) Targeting both directly to Mexican and Mexican American men who may be eligible, and to Latinas who could refer eligible male family members.
- 3) Posting and distributing flyers and advertisements in public areas, community organizations, and

community events with high traffic of Mexican and Mexican American men.

- 4) Posting and distributing flyers and advertisements on websites and on email list serves.
- 5) Going out into the community, such as by attending community events, health fairs, talk shows etc. to actively recruit and inform participants about the study. This will include doing presentations and collecting names and contact info of interested potential participants.
- 6) We will list our study on UCSD's CTRI ResearchMatch database and will use this resources to contact potentially interested participants.
- 7) Paid advertisements through print ads, web-based ads, radio, TV, and other venues.
- 8) We will be creating a Facebook business page exclusively for the advertisement of the Activo Study according to the IRB study guidelines.

Recruitment efforts will be not be limited to the Greater San Diego area, and will expand across the United States where applicable (websites, radio, TV, etc.)

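### Men are randomised individually with no visible household rule, although relatives may refer male family members and the texts prompt family activity: a control man could be exposed at home

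*Combined protocol and SAP*

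**What the plan says.** **Recruitment (Section 11).** One listed strategy is directed "to Latinas who could refer eligible male family members". On local physicians the plan adds: "These physicians will provide potentially eligible participants (or their family members) with information on the study". No limit per family or household is given. The other routes are mostly not family-based (flyers, websites and email lists, community events, a research registry, paid media, a Facebook page), and recruitment may reach beyond San Diego.

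**Intervention (Section 9, Treatment Conditions and Table 3).** The anticipated purposes of the texts include "5) inform about local events, 6) focus on the family, 7) provide social support". A sample message reads "Is the family home? Go on a walk together before dinner time". Printed manuals, feedback reports and tip sheets are also mailed over the six months.

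**Allocation (Section 9, Phase 2).** "We will randomize 60 MA men into a 6-month pilot trial", and at the baseline visit "participants will be randomly assigned to one of two conditions". The unit is the man. Household does not appear as a unit, a stratum or a restriction.

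**Eligibility (Section 9, Telephone Screening; Section 10).** The criteria cover age, ethnicity, phone ownership, current activity, and medical and psychiatric history. None concerns living with another participant.

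**Analysis (statistical text at the end of the document).** Six-month accelerometer minutes are regressed on arm, baseline value and confounders, with no household term. Retention and satisfaction are each judged against 80% and also compared between arms.

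**The concern.** Brothers, or a father and adult son, can both fall within ages 18 to 65 and both qualify. If they live together and are allocated to opposite arms, the control man belongs to the family that the other man's texts encourage him to be active with. He may also see the tailored mailings. This exposure would come through the intervention's intended mechanism, and the accelerometer would record any shared walks.

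The expected result is a smaller between-arm difference in activity. A control man who sees the other programme might also rate his own differently or be more likely to leave, which would affect the between-arm comparisons of satisfaction and retention. The pilot is meant to support a larger efficacy trial, so a diluted estimate could carry into its planning. If shared households are not recorded, the problem cannot be sized afterwards.

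**Working it through.** The readable text gives no derivation of the sample size and no household figures, so there is no stated calculation to reproduce. The following sizes the issue.

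**Inputs**
- 60 men randomised (Section 9). The allocation ratio is not stated; 1:1, or 30 per arm, is assumed.
- Illustrative effect: the six-month result of the larger print trial in Latinas (Table 1), 71.66 − 29.58 = 42.08 min/week, with SDs 89.92 and 84.37.
- Split pairs, *k*: not in the documents; varied from 0 to 3, with 10 as an extreme.
- Share of the effect passed to the exposed control man, *f*: not in the documents; varied from 0 to 1.

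**Chance that a co-resident pair is split.** With exactly 30 per arm: 30 × 30 / C(60,2) = 900/1770 = 0.51. Under simple randomisation it is 0.50. About half of any enrolled pairs would be split.

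**Dilution.** Expected difference = 42.08 × (1 − *f* × *k*/30). One split pair exposes 1/30 = 3.3% of control men, so with *f* no greater than 1 it costs at most 3.3%, or 42.08/30 = 1.4 min/week.

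| Split pairs | Loss, *f* = 0.5 | Loss, *f* = 1 | Difference, *f* = 1 (min/week) |
|---|---|---|---|
| 0 | 0% | 0% | 42.1 |
| 1 | 1.7% | 3.3% | 40.7 |
| 2 | 3.3% | 6.7% | 39.3 |
| 3 | 5.0% | 10.0% | 37.9 |
| 10 | 16.7% | 33.3% | 28.1 |

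**Against the trial's precision.** Pooled SD = √[(89.92² + 84.37²)/2] = 87.2. Standard error of the difference = 87.2 × √(2/30) = 22.5 min/week, giving a 95% half-width of about 45. Three split pairs with full carry-over shift the estimate by 42.08 − 37.87 = 4.2 min/week, or 4.2/22.5 = 0.19 standard errors. Power at two-sided 5% (assumed) would fall from about 46% to about 39%.

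**Household correlation.** Let ρ be the within-pair correlation and σ² the outcome variance. The variance of the difference in means is 2σ²/30 without pairs. Each same-arm pair adds 2ρσ²/30², and each split pair subtracts the same amount. The relative change is ρ × (same-arm pairs − split pairs)/30. Because about half the pairs split, its expectation is about zero under individual allocation.

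**The case against.** The strongest reply is that the whole chain is conditional. Two co-resident men must both qualify, both volunteer and be split. A woman who refers one husband or son creates no pair. The physician sentence concerns passing on information; it does not recruit families. Most routes are not family-based. All of this stands, and zero split pairs is a credible outcome.

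Full carry-over is also an upper limit. The intervention man has his own pedometer, goal setting, tailored feedback and interactive texts, and someone who joins a walk receives little of that. The control arm already receives some activity information and texts of its own. The family messages are samples for a programme still to be developed in Phase 1. These points stand too and push the loss toward the lower end of the range.

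The pilot's primary aim is feasibility and acceptability, with interest in the intervention arm. Exposure of control men does not change that arm's own rates against 80%, so only the between-arm comparisons and the efficacy estimate are affected.

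What survives is the gap itself: nothing in the readable eligibility or allocation text prevents a split household, and nothing records one. Some pages are not available for review, so a rule elsewhere cannot be fully excluded, but the visible lists where it would belong do not contain it.

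**Conclusion.** The concern holds as a minor design gap. Two men of one household could be split, and the control man may then be exposed. For 0 to 3 split pairs the loss is 0% to 10% of the effect, under 0.2 standard errors in the illustration. A large distortion would need many shared households: ten split pairs give 17% to 33% with half to full carry-over. These figures assume 30 men per arm and carry-over no greater than the whole effect. The minutes per week also borrow the effect and SDs of a different population.

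A reader might infer three stronger things that the documents do not support:
- **That control men are exposed.** No text says co-resident men will enrol, or how many.
- **That the bias always runs toward no effect.** That is the expected direction. A control man could react by doing less, and with so few men the estimate in one trial can move either way by chance.
- **That household correlation biases the planned model.** Same-arm and split pairs roughly cancel in the variance of the difference.

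**What to change.** Add one question to the Phase 2 telephone screen asking whether the man lives with someone already enrolled in Phase 2. Check his mailing address against those of enrolled men before randomisation; the study must hold these addresses in order to post its materials. Add the matching exclusion to Sections 9 and 10, enrol one man per household (the first to consent), and record how many shared-household volunteers came forward.

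The cost is a small amendment, one question and the loss of a few second volunteers. The rule does not cover relatives who live apart.

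If the sponsor prefers to keep second men, allocate co-resident men to the same arm and account for the clustering in the efficacy model. All pairs would then be same-arm, so the cancellation shown above no longer applies: each pair adds up to ρ/30 to the relative variance, at most 3.3%. The number of shared households should be reported under this option as well.

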10. HUMAN SUBJECTS

For Phase 1 we will recruit 48 participants and for Phase 2 we will recruit 60 participants. Participants in both phases will be sedentary (i.e., participating in moderate or vigorous physical activity two or less times per week for 30 minutes each time or less) men between the ages of 18-65 who self-identify as Mexican or Mexican-American. Participants in Phase 1 will participate in focus groups to guide development of the text-message components. Participants in Phase 2 will participate in a randomized clinical trial of a text-enhanced culturally and linguistically adapted, Spanish language, mail-delivered print intervention to promote physical activity.

Phase 1: Interested men will be telephone screened for eligibility. Interested and eligible men will be invited to attend a focus group to discuss preferences surrounding text-messages to increase physical activity. A randomly selected sub-sample of participants will be asked to return for a confirmatory panel. All participants will provide written consent to participate.

Phase 2: We will recruit men to enroll in a randomized controlled trial of the newly developed text-enhanced physical activity intervention compared to a publicly available, Spanish-language health education control, including PA, diet, and stress management information.

Eligibility Requirements for Phase 1 and 2: We will recruit men between the ages of 18-65 who self-identify as Latino and own a cell phone capable of sending and receiving text messages.

Exclusion criteria for Phase 1 and 2: To reduce the likelihood of injury participants will be screened with the Physical Activity Readiness Questionnaire. Potential participants with medical or psychological problems that could make adherence with the study protocol difficult or dangerous will not be included. Exclusions include history of coronary heart disease, history of myocardial infarction, currently engaging in more than 90 minutes of activity per week symptoms of angina, type I diabetes, uncontrolled hypertension, stroke, osteoarthritis, osteoporosis, orthopedic problems that would limit activity during the following six months, or any other serious medical condition that would make physical activity unsafe. Other exclusion criteria will include hospitalization due to a psychiatric disorder in the past 3 years, BMI above 45 kg/m, and/or taking medication that may impair physical activity tolerance or performance (e.g., beta blockers). The study physician will advise on medical questions that arise when screening for eligibility.

11. RECRUITMENT AND PROCEDURES PREPARATORY TO RESEARCH

Recruitment will follow a community-based, participatory model in that key community-based organizations and their leadership will be consulted and involved in recruitment. As in previous studies, we will employ multiple recruitment strategies. These strategies include:

- 1) We will recruit through local physicians (through the UCSD Department of Family Medicine) whose patient populations are largely Mexican and Mexican-American. Some of these physicians are Latino and bilingual. These physicians will provide potentially eligible participants (or their family members) with information on the study.
- 2) Targeting both directly to Mexican and Mexican American men who may be eligible, and to Latinas who could refer eligible male family members.
- 3) Posting and distributing flyers and advertisements in public areas, community organizations, and

community events with high traffic of Mexican and Mexican American men.

- 4) Posting and distributing flyers and advertisements on websites and on email list serves.
- 5) Going out into the community, such as by attending community events, health fairs, talk shows etc. to actively recruit and inform participants about the study. This will include doing presentations and collecting names and contact info of interested potential participants.
- 6) We will list our study on UCSD's CTRI ResearchMatch database and will use this resources to contact potentially interested participants.
- 7) Paid advertisements through print ads, web-based ads, radio, TV, and other venues.
- 8) We will be creating a Facebook business page exclusively for the advertisement of the Activo Study according to the IRB study guidelines.

Recruitment efforts will be not be limited to the Greater San Diego area, and will expand across the United States where applicable (websites, radio, TV, etc.)

